**Palatal Wound Healing Evaluation After
Application of Platelet Rich Fibrin Versus 0.2%
Hyaluronic Acid Dressings
(Randomized Controlled Clinical Trial)**

Methodology

Date: 12/5/2020

Sample selection and assignment:

Thirty patients (16 females and 14 males) who were candidates for free gingival grafting surgery participated in this prospective clinical trial.

The subject were recruited consecutively from the outpatient clinic of Oral Medicine, Periodontology, oral Diagnosis and Radiology Department, Faculty of Dentistry, Ain Shams University .The purpose of the study was explained to all patients and an informed consent was signed before the conduction of the study. The proposal was presented to the faculty of Dentistry Ain Shams University Research Ethics committee and was approved before starting the research with number (566). Also the study was registered in clinical trial registration site (NCT).

Patient selection:

Inclusion Criteria:

- Patients who were indicated for soft tissue augmentation with free gingival graft for mucogingival surgery or for implant therapy.

Material and Method

- Age range (20-50) years.
- Good patient compliance with the plaque control instructions following initial therapy.

Exclusion criteria:

- Presence of systemic diseases which could influence the outcome of the therapy.
(American Society of Anesthesiologists I; ASA I)
- Smoker patients.
- Pregnant and lactating females.
- Vulnerable group of patients (prisoners, handicapped, decisionally impaired individuals).

Grouping Criteria:

The study consisted of three groups; the number of patient in each group was determined by sample size calculation based upon the results of *Yildirim et al. 2017*. Using alpha level of 0.05 (5%) and β level of 0.20 (20%) i.e. power = 80%; the estimated minimum required sample size was approximately 10 cases in each group. Patients were randomly selected using computer generated randomization (www.randomizer.org). Allocation concealment was achieved using a sealed coded opaque envelope containing treatment of the subject

Group I(10 patients):

Patients received platelet rich fibrin as a palatal dressing after free gingival graft harvesting.

Group II(10 patients):

Patients received hyaluronic acid* gel 3-4 times per day as a palatal dressing after free gingival graft harvesting.

Group III(10 patients) (Control group) :

Patients received gel foam as a palatal dressing after free gingival graft harvesting

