Categorical data were presented as frequencies and percentages and were analyzed using chi square test. Numerical data were tested for normality using Shapiro-Wilk test and were presented as mean and standard deviation values. Parametric data were analyzed using one-way ANOVA followed by Tukey's post hoc test for intergroup comparisons and one-way repeated measures ANOVA followed by Bonferroni post hoc test for intragroup comparisons. Non-parametric data were analyzed using Kruskal-wallis test followed by pairwise comparisons utilizing Mann Whitney U test with Bonferroni correction for intergroup comparisons and Friedman's test of repeated measures followed by multiple pairwise comparisons utilizing Wilcoxon signed-rank test with Bonferroni correction for intragroup comparisons. The significance level was set at $p \leq 0.05$ within all tests. Statistical analysis was performed with IBM® SPSS® Statistics Version 26 for Windows.

® IBM Corporation, NY, USA.

®SPSS, Inc., an IBM Company.

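### For three arms, the Bonferroni correction of the between-arm Mann-Whitney tests is valid but needlessly conservative; Holm, or a binding Kruskal-Wallis gate, recovers power at no cost in patients.

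*Protocol*

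**What the plan says.** Grouping Criteria in the Protocol fixes the structure: "The study consisted of three groups", with 10 patients in each (platelet rich fibrin, hyaluronic acid, gel foam control). The size is justified by 5% alpha and 80% power: "the estimated minimum required sample size was approximately 10 cases in each group". That section refers to a published study for its basis. It gives no effect size or SD and mentions no pairwise correction.

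IV-Statistical analysis sends each numerical outcome down one of two routes after a Shapiro-Wilk test.

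- Parametric route: "Parametric data were analyzed using one-way ANOVA followed by" Tukey's test.
- Rank route: "Kruskal-wallis test followed by pairwise comparisons utilizing Mann Whitney U test with Bonferroni correction for intergroup comparisons".

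All tests use p ≤ 0.05. The text implies that the pairwise tests come after the three-arm test, but does not say that they depend on its being significant. Within-group comparisons over time have their own Bonferroni correction.

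**The concern.** The question in the trial's title, platelet rich fibrin against 0.2% hyaluronic acid, is one of three pairwise comparisons, with 10 patients on each side. On the rank route that comparison follows a three-arm test at 0.05 and is then tested at 0.05/3. With three arms the two layers together protect more than the 5% level needs, and power is lost in exchange.

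The rank route may well matter here. Pain is a 0 to 10 score and healing is an index, so either could fail the normality test. The Protocol does not say in advance which route an outcome will take.

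**Working it through.** **Inputs.** From the Protocol: three arms, 10 per arm, level 0.05, 80% power. Assumed: two-sided tests, normal data with equal SD, and a shift of 1.325 SD. The Protocol's figure of about 10 per group cannot be reproduced without an effect size, so it was inverted: 1.325 SD is the shift that a two-sample t-test at two-sided 0.05 detects with about 80% power at 10 per arm.

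**Why three arms are special.** There are 3 pairwise nulls. If any two are true, all three arms are equal, so only two null situations exist.

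1. All arms equal. With a binding gate, no pair can be declared different unless Kruskal-Wallis is significant, which has probability at most about 5%.
2. One arm differs. One true pairwise null is left. Testing it at 0.05 holds 5%.

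This is closed testing. It does not carry over to four or more arms.

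**Critical values, exact Mann-Whitney, 10 against 10.**

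- Bonferroni: 0.05/3 = 0.0167, met by U ≤ 18 (p = 0.0147).
- Gated, uncorrected: 0.05, met by U ≤ 23 (p = 0.0433).
- Holm: smallest p-value at 0.05/3, next at 0.05/2 = 0.025, largest at 0.05, stopping at the first failure. The first step equals Bonferroni and later steps are easier, so every Bonferroni rejection is kept.

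**Simulated power for a shifted pair, one arm shifted by 1.325 SD.**

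| Procedure on ranks | Power |
|---|---|
| Kruskal-Wallis, then Bonferroni | 57.9% |
| Holm | about 62% |
| Kruskal-Wallis, then exact Mann-Whitney at 0.05 | 71.0% |

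Holm gains 62 − 58 = about 4 points; the gated procedure gains 71.0 − 57.9 = 13.1.

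**Dependence on the assumed pattern (gated against Bonferroni).**

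| Pattern of means (SD units) | Pair | Bonferroni | Gated | Gain, points |
|---|---|---|---|---|
| 1.0, 0, 0 | shifted | 32.6% | 44.0% | 11.4 |
| 1.5, 0, 0 | shifted | 70.9% | 82.5% | 11.6 |
| 1.325, 0.662, 0 | extreme | 57.2% | 65.3% | 8.1 |
| 1.325, 0.662, 0 | adjacent | 13.4% | 24.3% | 10.9 |
| 2.65, 1.325, 0 | adjacent | 58.2% | 75.6% | 17.4 |

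Where a pair is detected almost always, the gain is near zero. With scores rounded to whole points from 0 to 10, ties included, the gain at 1.325 SD remained (58% to 72%).

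**Family-wise error on ranks.** Gated: 4.7% with all arms equal and 4.0 to 4.4% with one arm different (4.8 to 4.9% for the rounded scores). Bonferroni after Kruskal-Wallis: 3.5% and about 1.5%. Without the gate, uncorrected Mann-Whitney tests give about 11 to 13%; for three independent tests the figure would be 1 − 0.95³ = 14.3%.

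**Parametric route.** With equal variances, F then pooled t at 0.05 also holds about 5%, and power rises from 68.0% with Tukey to 76.8%. The pooled t-test, however, borrows the third arm's SD. With the differing arm 3 SD away and its SD half that of the others, the false-positive rate for the truly equal pair is about 9% with pooled t, against about 4.5% with Tukey. Each Mann-Whitney test uses only its own two arms, and the rank-route error stayed at or below about 4.6% when the differing arm's SD was changed.

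**The case against.** **The plan is valid as it stands.** Bonferroni-corrected Mann-Whitney tests after Kruskal-Wallis are standard and control error with or without a gate. That is right: this is avoidable loss of power, not an error-rate fault.

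**The uncorrected alternative depends wholly on the gate.** The Protocol does not state the gate explicitly, and without it the error exceeds 10%. This stands as a condition on the gated fix, whose wording must make the gate binding. It does not touch Holm.

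**Nothing else in the plan controls multiplicity.** Pain alone is recorded at six times, and no correction is made across outcomes or times. With one arm truly different, moving the remaining pair from 1.5% to 5% would, over six independent looks, raise the chance of at least one false claim from 1 − 0.985⁶ = 8.7% to 1 − 0.95⁶ = 26.5%. Repeated looks at the same patients are not independent, so this is only an illustration. The cost is real and should be weighed.

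**The size rests on an assumed effect and normal data**, although the rank route is for data judged non-parametric. This stands. The direction does not depend on the assumption; the number of points does.

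A reader might go further and infer that Tukey after ANOVA is equally unnecessary. That does not follow: the argument there needs equal variances, and the Protocol states a normality test but no variance check. A reader might also infer that the within-group Bonferroni can go. Six time points give 15 pairs, and closed testing does not reduce these to one remaining null: with one time point different, uncorrected tests gave about 31% family-wise error.

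**Conclusion.** The point holds for the between-arm rank comparisons only. Bonferroni is valid there but stricter than three arms require. At an assumed one-arm shift of 1.325 SD, Holm recovers about 4 points of power and a binding Kruskal-Wallis gate about 13. Over the other patterns tabulated, the gated gain runs from about 8 to 17 points, and it vanishes for pairs that are detected almost always. Error within one outcome and time point stays at or below 5% with either replacement.

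The figures do not show that the planned 80% power is wrong. The Protocol does not say which effect or which test that power refers to, so 58% is a comparison at an assumed shift and not a correction of the sample size.

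**What to change.** In IV-Statistical analysis, change the between-arm rank comparisons in one of two ways.

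- **Minimum:** replace Bonferroni with Holm for the three Mann-Whitney tests. No gate is needed, and no pair that Bonferroni would reject is lost.
- **Larger gain:** write: *If Kruskal-Wallis is significant at 0.05, each pair is tested by exact Mann-Whitney at 0.05; if it is not, no pair is declared different.* The second clause is essential.

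Keep Tukey on the ANOVA route and Bonferroni for the within-group comparisons over time.

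The cost is one sentence, with no patients and no data. No simultaneous confidence intervals are lost, since the Protocol plans none. When one arm truly differs, the false-positive rate for the remaining pair rises from about 1.5% to at most 5% per outcome and time point. The report should say that no correction is made across outcomes and times.

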4. The PRF clot was removed from the tube using sterile tweezers, separating it from the RBC base by using a lancet. It was compressed between two sterile glass slabs and wrapped within sterile gauze moistened with saline.
5. The thickness of the palatal tissue was measured at three different points; each point was located at the middle of 1st, 2nd premolar and 1st molar 7mm from the gingival margin.
6. Free gingival graft was harvested from the palate and its thickness was measured.
7. The PRF membrane was placed as a palatal dressing and fixed in place by X suture using 5-0 polypropylene**.

** Assut Sutures, non Absorbable (Polypropylene) 5-0 USP, braided violet coated 3/8 rev.cutt.17mm, AM trading, Switzerland

Group 2:

1. Anesthesia (Articaine HCL 4% containing epinephrine at a concentration of 1:100,000)^{††} was administrated at to the palate where a free gingival graft was harvested.
2. The thickness of the palatal tissue was measured at three different points; each point was located at the middle of 1st, 2nd premolar and 1st molar 7mm from the gingival margin.
3. Free gingival graft was harvested from the palate and its thickness was measured.
4. Gel foam was cut according to the graft's dimensions to act as a carrier for the hyaluronic acid^{‡‡}that was used as a palatal dressing.
5. Gel foam was fixed in place using X suture using §§5-0 polypropylene.

^{††}Artinibsa 4%cartouches de 1.8ml ,inibisa dental.

^{‡‡}Gengigel 0.2% oral gel 20ml Riceerfarma Milano Italy.

§§ Assut Sutures, non Absorbable (Polypropylene) 5-0 USP, braided violet coated 3/8 rev.cutt.17mm, AM trading, Switchezland

Group 3:

1. Anesthesia (Articaine HCL 4% containing epinephrine at a concentration of 1:100,000)^{***} was administrated at to the palate where a free gingival graft was harvested.
2. The thickness of the palatal tissue was measured at three different points; each point was located at the middle of 1st, 2nd premolar and 1st molar 7mm from the gingival margin.
3. Free gingival graft was harvested from the palate and its thickness was measured.
4. Gel foam was cut according to the graft's dimensions and used as a palatal dressing.
5. Gel foam was fixed in place using X suture using 5-0 polypropylene^{†††}.

^{***} Artinibsa 4% cartouches de 1.8ml ,inibisa dental.

^{†††} Assut Sutures, non Absorbable (Polypropylene) 5-0 USP, braided violet coated 3/8 rev.cutt.17mm, AM trading, Switchezland

Material and Method

V-Postoperative care:

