- Oral hygiene instructions was given , antibiotic (Augmentin^{†††} 1 gm every 12 hours, metronidazole^{§§§} 500 mg every 12 hours) , anti-inflammatory and analgesics(Brufen^{****} 400 every 12 hours) was prescribed for the patient and instructed to avoid brushing at the surgical site only rinsing with hot saline mouthwash.
- Patient was recalled for assessment and follow up, sutures was removed after 1 week.

^{†††} Augmentin 1gm,Medical union pharmaceuticals(MUP) Egypt under license from ,Glaxosmithkline

^{§§§}Flagyl 500 mg, sanofi Aventis Egypt under license of sanofi Aventis French

^{****} Brufen 400mg, Al kahira pharm. and chem.Ind.Co. under license from abbott laboratories

VI-Postoperative evaluation and assessment:

- Patients were asked to assess their pain sensation and bleeding at 1st, 3rd, 7th 14th, 21st and 30th days using the visual analogue scale (VAS). The visual analogue scale score by Price et al 1983 for pain ranged from 0 (no pain) to 10 (sever pain), while bleeding was scored as 0(not present) and 1(present).
- The Healing index scale by *Landry et al. 1988* was used to assess the palatal wound healing, where in this index tissue color, response to palpation, presence of granulation tissue presence of suppuration and epithelization of the incision margin were recorded.
- The color of the palatal mucosa was assessed by comparing it to the adjacent and opposite side by taking pictures and using the image J program at 3rd,7th, 14th, 21st and30th days.
- The thickness of the palatal mucosa was measured preoperative and 4 weeks postoperative by a graduated periodontal probe.

IV-Statistical analysis:

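### Palatal thickness has two time points, where the prescribed Friedman test is only a sign test; Wilcoxon signed-rank should be named directly for it (minor, within-arm, rank route only)

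*Protocol*

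**What the plan says.** Under the statistical analysis heading, the protocol chooses between two routes by a normality check: "Numerical data were tested for normality using Shapiro-Wilk test". Within an arm, the parametric route uses "one-way repeated measures ANOVA followed by Bonferroni post hoc test for intragroup comparisons". The rank route uses "Friedman's test of repeated measures followed by multiple pairwise comparisons utilizing Wilcoxon signed-rank test with Bonferroni correction for intragroup comparisons". Neither rule separates outcomes by their number of time points, and the level is 0.05 for every test.

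Under both the assessments heading and the postoperative evaluation heading, the thickness outcome has two readings: "The thickness of the palatal mucosa was measured preoperative and 4 weeks postoperative by a graduated periodontal probe". The surgical protocol adds that "The thickness of the palatal tissue was measured at three different points". How the three points are combined is not stated. On arm size, the grouping section says that "the estimated minimum required sample size was approximately 10 cases in each group".

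**The concern.** Friedman's test is an omnibus test for three or more related measurements. With two, each patient's ranks are 1 and 2, so the test sees only whether thickness went up or down and discards by how much. The Wilcoxon signed-rank test uses the size of the change, and the protocol already names it, but as the follow-up to Friedman. Read in the usual omnibus-then-post-hoc way, the weaker test decides whether the stronger one is looked at. An arm whose donor site has clearly changed in thickness by Wilcoxon could then be reported as showing no significant change. If instead both tests are always run, one before-after comparison yields two p-values that can disagree, and the text does not say which decides.

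**Working it through.** **Inputs from the protocol.** Two time points for thickness; 10 patients per arm; significance at p ≤ 0.05; route chosen by Shapiro-Wilk. The size, SD and distribution of the thickness change and the probe graduation are not given, so everything under step 4 is assumption. The protocol has no power figure for this comparison to reproduce. Its sample size is stated without an effect size, so it can be neither confirmed nor refuted and does not bear on this point.

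**Step 1: what Friedman becomes.** For k = 2, n patients, no ties and rank sums R1 and R2:

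Q = 12/(n·2·3)·(R1² + R2²) − 9n = (increases − decreases)²/n, referred to chi-square with 1 df.

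| Split of 10 | Q | Friedman p | Exact sign test p |
|---|---|---|---|
| 7:3 | 16/10 = 1.6 | 0.206 | 0.344 |
| 8:2 | 36/10 = 3.6 | 0.058 | 0.109 |
| 9:1 | 64/10 = 6.4 | 0.011 | 0.021 |
| 10:0 | 100/10 = 10 | 0.002 | 0.002 |

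**Step 2: true level.** Rejection needs 9:1 or 10:0 in either direction: 2 × (1 + 10)/1024 = 22/1024 = 2.1%. The exact Wilcoxon test at n = 10 rejects when the smaller rank sum W is at most 8 (p = 0.049), so it uses nearly the full 5%.

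**Step 3: cases where the two disagree.**
- 8:2, with the two exceptions the smallest changes: W = 1 + 2 = 3. Five rank subsets have a sum of at most 3, so exact p = 2 × 5/1024 = 0.010. Friedman p = 0.058.
- 7:3, with the three exceptions the smallest: W = 6, exact p = 28/1024 = 0.027. Friedman p = 0.206.

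**Step 4: power, under assumptions.** Shifts are in SDs of the paired change, n = 10, two-sided 0.05.

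*All samples, normal changes without ties, ignoring the normality check.* Wilcoxon alone against Friedman-then-Wilcoxon is 60% against 33% at 0.8 SD and 79% against 51% at 1.0 SD. The Friedman part can be checked by hand. At 0.8 SD a change is positive with probability 0.788, so at least 9 of 10 has probability 0.788¹⁰ + 10 × 0.788⁹ × 0.212 = 0.34.

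*Following the plan's path.* Only samples failing Shapiro-Wilk reach Friedman (the check is assumed to be applied to the differences). At 0.8 SD:

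| Shape of change | Share sent to rank route | Loss on that route (points) | Loss over full path (points) |
|---|---|---|---|
| Normal | 5% | 19 | 1.0 |
| Laplace | 15% | 8 | 1.3 |
| t, 3 df | 18% | 9 | 1.6 |
| Right-skewed exponential | 44% | 37 | 16 |

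The last column is, up to rounding, the product of the two before it (for example 0.44 × 37 = 16). At 1.0 SD the full-path losses are 0.8, 1.4, 1.1 and 0.0 points. The last is zero because at that shift every exponential change is positive and both tests always reject. For a left-skewed exponential the loss on the route is 11 to 17 points. With the same 44% routed, that is 0.44 × 11 to 0.44 × 17, or about 5 to 7 points overall.

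*Probe readings.* Normal changes rounded to steps of 1, 0.5 or 1/3 mm lose about 0 to 11 points on the rank route; the coarser the steps, the smaller the loss. Zeros also soften the gate: 7:1 with two zeros gives Q = 36/8 = 4.5, p = 0.034, against 0.070 for the exact sign test. The 2% level in step 2 therefore holds only without ties.

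**The case against.** The strongest reply is that little depends on this. The trial compares three dressings, and the between-group tests are specified separately and untouched. Within-arm change does not compare dressings. The error is conservative, so it creates no false positive. Most samples of ten go to the parametric route, where two-level repeated measures ANOVA equals the paired t-test and nothing is lost. All of that stands, and it is why the point is minor.

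A second reply is that the gate is inferred. The protocol never says that Wilcoxon is run only after a significant Friedman test. That is correct, and a reader who takes the blocking as a stated rule goes further than the text. But the same phrasing links ANOVA to Tukey and Kruskal-Wallis to Mann-Whitney, so omnibus-then-post-hoc is the natural reading. On the other reading the plan still leaves two competing p-values for one comparison.

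A third reply is that the sentence is a template for the outcomes with many visits, and that matching tests to outcomes may be left to an analysis plan that is not shown. The absence of such matching is indeed no fault. The point is narrower: the rule as stated covers thickness and assigns it a poorly suited test.

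A reader might also infer a fixed, substantial power loss from the normal-data figures (60% against 33%). The documents do not support that. They give no effect, SD, shape or graduation, and those figures ignore both the normality check and ties.

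**Conclusion.** The point holds in limited form. That Friedman is a sign test here, that it needs 9 of 10 in one direction, and that its level is about 2% follow from the visit schedule and arm size alone, given no ties. That it can override a significant Wilcoxon result depends on reading it as a gate. The power loss depends on assumptions throughout: about 0 to 37 points on the rank route at 0.5 to 1.2 SD, about 0 to 11 there with normal changes rounded to probe-like steps, and usually 1 to 2 over the full path, more only if changes are strongly skewed. It concerns within-arm thickness change on the rank route and nothing else. It gives no ground for doubting the comparison of dressings. Minor priority, worth doing because the better test is already in the plan.

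**What to change.** Add one sentence to the statistical analysis section: for outcomes with two time points (palatal thickness), the non-parametric intragroup test is the Wilcoxon signed-rank test alone, without a preceding Friedman test. Bonferroni can be dropped from that sentence, since with one pair the correction factor is 1 and changes nothing. Keep Friedman with its follow-up for outcomes with three or more time points, such as pain and colour. The change needs no new data, software or patients, and leaves the parametric route and the between-group tests as they are.

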*Gengiegel 0.2% oral gel 20ml Riceerfarma Milano Italy.

III- Assessments:

1-Clinical parameters:

- Subjective assessment**

-Patients were asked to assess their pain sensation and bleeding at 1st, 3rd, 7th 14th, 21st and 30th days using the visual analogue scale (VAS). The visual analogue scale score by Price et al 1983 for pain ranged from 0 (no pain) to 10 (severe pain), while bleeding was scored as 0(not present) and 1(present) (***Price et al.1983***).

- Objective assessment**

-The Healing index scale by ***Landry et al.1988*** was used to assess the palatal wound healing, where in this index tissue color, response to palpation, presence of granulation tissue presence of suppuration and epithelization of the incision margin were recorded.

-The color of the palatal mucosa was assessed by comparing it to the adjacent and opposite side by taking pictures and using the image J program at 3rd, 7th, 14th, 21st and 30th days (***Pei-Nan et al.2012***).

- The thickness of the palatal mucosa was measured preoperative and 4 weeks postoperative by a graduated periodontal probe.

Material and Method

[figure not shown]

Fig (1): Palatal thickness measurements at 3 different points the middle of 1st, 2nd premolar and 1st molar 7mm from the gingival margin

IV-Surgical protocol:

A) Pre surgical procedures

Scaling and root planning was done; oral hygiene instructions was given to the patient to follow them.

B) Surgical procedures

Group 1:

1. Anesthesia (Articaine HCL 4% containing epinephrine at a concentration of 1:100,000)[†] was administrated at to the palate where a free gingival graft was harvested.
2. Just prior to surgery a 10 ml intravenous blood was obtained from the median antecubital vein of the patient in order to be divided into two 5 ml glass tubes[‡] without additives to be [§]centrifuged immediately at 2700 revolutions per minute for 12 minutes or in one 10 ml glass test tube without additives were centrifuged immediately at 3000 revolutions per minute for 10 minutes at room temperature.

[†] Artinibsa 4% cartouches de 1.8ml ,inibisa dental.

[‡] Dry Vacutube, Biocon®, Brazil

[§] PRF CENTRIFUGE (Duo machine), UNSPSC code 41100000 (Ostralos Ltd, New Zealand)

Material and Method

3. Coagulation started immediately and three parts quickly appear in the tube: a packed red blood cell at the bottom, acellular plasma at top and the PRF clot in between.

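### If pain takes the non-parametric route, Bonferroni over 15 day-pairs with 10 patients per arm passes an exact two-sided Wilcoxon test only when all 10 change the same way; exact p-values with Holm lose less

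*Protocol*

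**What the plan says.** Under IV-Statistical analysis, the protocol checks numerical data with the Shapiro-Wilk test. If they are judged non-parametric, changes over time within an arm are tested with Friedman's test and then "multiple pairwise comparisons utilizing Wilcoxon signed-rank test with Bonferroni correction for intragroup comparisons". Arms are compared by Kruskal-Wallis and then "pairwise comparisons utilizing Mann Whitney U test with Bonferroni correction for intergroup comparisons". The level is 0.05 for every test. The section does not give the number of day-pairs, the sidedness, or whether p-values are exact or approximate.

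Two further facts fix the size of the problem:

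- Pain has six time points. Under VI-Postoperative evaluation and assessment: "Patients were asked to assess their pain sensation and bleeding at 1st, 3rd, 7th 14th, 21st and 30th days". The Subjective assessment part of section III has the same schedule.
- Each arm has 10 patients. Under Grouping Criteria: "the estimated minimum required sample size was approximately 10 cases in each group".

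**The concern.** A signed-rank test on 10 pairs has few attainable p-values, and the smallest is not far below a threshold divided by 15. The correction may then demand near-perfect agreement among patients before any day-pair is called different.

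The post hoc tests exist to show between which days pain changed within an arm. If one patient who is unchanged or moves the other way is enough to lose a pair, a non-significant result says little about whether pain changed. Unchanged scores are plausible late in follow-up, when patients may sit at 0 on both days, although the protocol gives no pain data to show how often.

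**Working it through.** **Inputs from the protocol.** Six pain days (1, 3, 7, 14, 21, 30); 10 patients per arm; level 0.05; Wilcoxon with Bonferroni within each arm. The one calculated figure in the document, about 10 per group, cannot be reproduced because no effect size or SD is given. It is used here only as n = 10.

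**Assumptions.** Pain is judged non-parametric; tests are two-sided; all pairs are tested, with each arm as its own family; unchanged scores are dropped.

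**Threshold.** Pairs = 6 × 5 / 2 = 15, so each pair needs p ≤ 0.05/15 = 0.00333.

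**Exact p-values.** With n non-zero changes there are 2^n equally likely sign patterns under the null. W is the smaller rank sum.

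| Outcome for a day-pair | Exact two-sided p | × 15 | Passes? |
|---|---|---|---|
| All 10 change the same way (W = 0) | 2/1024 = 0.00195 | 0.029 | yes |
| Smallest change is a reversal (W = 1) | 4/1024 = 0.00391 | 0.059 | no |
| W = 2 | 6/1024 = 0.00586 | 0.088 | no |
| One unchanged or missing, other 9 agree | 2/512 = 0.00391 | 0.059 | no |

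Ties do not rescue a reversal. Over all 512 tie patterns at n = 10, the smallest exact p with at least one reversal is 0.00391.

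If the tests were one-sided, untied reversals up to W = 2 would pass (3/1024 = 0.00293; × 15 = 0.044).

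**Normal approximation.** For n = 10, W = 0 and no ties, the mean is 10 × 11 / 4 = 27.5 and the SD is √(10 × 11 × 21 / 24) = 9.81. So z = −2.803, p = 0.00506, and × 15 = 0.076: a unanimous change fails. With the tie-corrected variance, only 9 outcomes pass at n = 10, one at n = 9 and none at n = 8. All of them have at least 8 changes of equal size.

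**Holm with exact p-values.** The first step is still 0.05/15, so a unanimous pair is needed to start. After k rejections the multiplier is 15 − k:

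- A pair at 0.00391 gives 0.00391 × 14 = 0.055, × 13 = 0.051, × 12 = 0.047. It passes once three other pairs have passed.
- W = 2 gives 0.00586 × 8 = 0.047. It passes once seven others have passed.

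**Between-arm contrast.** Mann-Whitney with 10 against 10 has minimum p = 2/184,756 = 0.0000108; × 3 pairs = 0.00003. The same correction costs little there.

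**Illustration under assumed inputs.** The protocol gives no pain means, SDs or score steps. Simulations used 24 settings of 1,000 arms each: day-1 mean 7, 5, 3 or 2, falling to 0.2 or less by day 30; three SD levels (day-1 between-patient 1.0 and within-patient 1.2, both × 0.6, × 1.0 or × 1.4, shrinking with the square root of the mean); whole-number or 0.1-step scores clipped to 0–10.

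| Mean significant pairs of 15 | Range over settings |
|---|---|
| Exact p, Bonferroni | 0.1 to 12.9 |
| Exact p, Holm | 0.1 to 14.5 |
| Normal approximation, Bonferroni, 0.1-step scores | 0.00 in all 12 settings |
| Normal approximation, Bonferroni, whole numbers | 0.00 to 0.99 |

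Holm added 0 to 3.1 pairs on average, found at least one extra pair in 1% to 98% of arms, and lost none in 24,000 arms. The gain is small when pain is low relative to its spread. With the middle SD and whole numbers, the average total rose from 1.7 to 2.3 pairs at day-1 mean 3, and from 0.41 to 0.47 at mean 2. The family-wise error of exact Holm was 0.4% to 4.0% in eight full or partial null settings of 2,000 arms each.

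**The case against.** The strongest reply is that nothing here is wrong. Bonferroni after Friedman is valid and conservative, and preferring Holm could be urged against almost any plan. That is why the point is minor. It is more than a general preference because the loss follows from this trial's own numbers: at n = 10 with 15 pairs, the threshold falls between the two smallest attainable exact p-values.

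The result is also conditional. It needs pain to take the non-parametric route, two-sided tests and all 15 pairs. If only the five comparisons with day 1 were tested, exact results up to W = 3 would pass (0.00977 × 5 = 0.049), as would one unchanged patient with nine agreeing (0.00391 × 5 = 0.020). That is correct, but the protocol names no such subset. A wider family would be worse: over all three arms the threshold is 0.05/45 = 0.00111, below the smallest attainable 0.00195, so nothing could pass.

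The unanimity rule is specific to pain. Colour has five days and 10 pairs, so W = 1 passes (0.00391 × 10 = 0.039). This stands, though Holm is equally sound for the other within-arm outcomes.

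The choice between exact and approximate p-values may be settled in a statistical analysis plan that is not shown. The protocol's silence on it is therefore not the defect. The protocol does fix Bonferroni, but replacing it alone would achieve little if approximate p-values were used.

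Finally, the remedy is partial and its gain in this trial is unknown, since the simulated range is wide and rests on assumed inputs. That also stands.

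**Conclusion.** The concern holds as a minor, avoidable loss of power. Given the non-parametric route, two-sided tests and all 15 pairs within an arm, the exact results depend only on n = 10 and the number of pairs: 0.029 if all 10 agree, at least 0.059 otherwise. How many pairs Holm would recover cannot be known from the protocol. Its reach is confined to within-arm pain comparisons; Friedman's test and every comparison between dressings are unaffected.

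**What to change.** In IV-Statistical analysis, state that the within-arm Wilcoxon p-values are exact, and replace Bonferroni with Holm over the same day-pairs for those comparisons. The between-arm wording can stay.

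The cost is one line of text. No day-pair is dropped and no data are added. Moving from Bonferroni to Holm costs nothing for the same p-values. Moving from approximate to exact p-values has a small cost in a few heavily tied patterns: nine equal changes plus one unchanged score, or plus one smaller reversal, pass Bonferroni under the normal approximation (0.041 and 0.049) but not exactly (0.059).

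The protocol is written in the past tense. If within-arm results have already been seen, the change should be reported as made afterwards.
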